4.2.3 Additional Safety Assessments

4.2.3.1 Laboratory Data

Selected laboratory parameters for safety reporting will be described further in the OLE population by summarizing the marked abnormalities and shift tables. Marked abnormalities will be identified according to a Sponsor-defined standard, which generally captures post-baseline laboratory values both outside a reference range and achieving a threshold percent change from baseline. Where needed, laboratory values will be linearly transformed to a standard reference range in order to account for intrinsic differences between males and females or measurement differences between laboratory standards.

Laboratory abnormalities and the patient's worst Common Terminology Criteria for Adverse Events (CTCAE) grade during study will be summarized for hematology and serum chemistry parameters, in addition to change from Baseline summaries.

Elevated liver enzyme tests will be summarized by the following upper limit of normal (ULN) categories as these are indicators of severe liver injury:

- ALT or AST>3ULN and total bilirubin>2 ULN as defined by Hy's law
- ALT or AST>3 ULN

4.2.3.2 Vital Signs

Vital signs will be summarized using summary statistics and change from baseline. The proportion of patients experiencing clinically significant changes relative to baseline will be reported if appropriate.

4.2.3.3 ECGs

A shift table for the qualitative ECG assessments will be produced, summarizing the Baseline and worst post-baseline results.

4.2.3.4 Medical History

Medical history data collected in the electronic-CRF (eCRF) from OLE Day 1 will be summarized using summary statistics, reporting the proportion of patients with at least one medical condition and the total number of medical conditions. The medical conditions will then be split out by type.

4.2.3.5 Concomitant Medications

Concomitant medications include any medication being used at any time from first dose of OLE study drug through to 7 days after last dose of OLE study drug. The data will be summarized, and report the total number of patients taking at least one medication, and total number of medications. Summaries will also be split by medication class and preferred medication. Medication terms will be mapped and reported using the WHO drug dictionary.

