
At any time during the study, patients who have worsening UC may receive concomitant therapy with corticosteroids (IV, oral, or topical). Addition of or increases in doses of 5-ASA (oral or topical) and/or initiation of immunosuppressant treatment (i.e., AZA, 6-MP, or MTX), including patients from Study GA27927, is also permitted during this study at the discretion of the investigator.

Patients who are taking immunosuppressants (i.e., AZA, 6-MP, or MTX) as part of their concomitant treatment in the Phase II OLE and Phase III controlled studies may continue to receive immunosuppressants in OLE-SM study with dose adjustments at the discretion of the investigator. Generally accepted criteria for discontinuation of immunosuppressants due to toxicity include, but are not limited to, acute pancreatitis, severe leukopenia, severe thrombocytopenia, or clinically significant elevations of the liver-associated enzymes from baseline, especially in the presence of an elevated total bilirubin. The ultimate decision to reduce dose or discontinue immunosuppressants due to toxicity or any other reason remains at the discretion of the investigator.

Rescue Therapy That CANNOT Be Given with Study Medication

At ANY time during the conduct of the study, use of other immunosuppressive agents including, but not limited to, other anti-integrins, T or B cell depleters (except AZA and 6-MP), TNF inhibitors (including TNF inhibitor biosimilars), anti-adhesion molecules, cyclosporine, tacrolimus, *Janus kinase (JAK) inhibitors*, or investigational agents are prohibited. Patients who do receive such rescue therapies are not allowed to receive further etrolizumab treatment and are to be withdrawn into the 12-week safety follow-up. These patients will then enter Part 2 (SM) of the OLE-SM study for 92 weeks of extended PML monitoring.

Moving from Part 1 (Open-Label Extension) to Part 2 (Safety Monitoring) in this Study

Patients who discontinue treatment with open-label etrolizumab will be requested to enter a post-treatment 12-week safety follow-up, and then be requested to enter Part 2 (SM) of this study. Part 2 (SM) will consist of an additional 92 weeks of extended PML monitoring following the initial 12-week safety follow-up period. See [Figure 1](#) and [Figure 2](#) for schemas of the study and see Section [3.1.1.2](#).

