5.1.1.7 Decreased Effectiveness of Immunizations

Background

The effect of etrolizumab upon the efficacy of vaccinations is unknown.

Patient Selection and Risk Mitigation

Patients who received a live attenuated vaccine during the Phase II OLE or Phase III studies or within 4 weeks prior to enrollment in the OLE are excluded from the study. Patients should not receive live attenuated vaccines during the study and for approximately 5 half-lives (approximately 12 weeks) after final study drug administration.

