Appendix 2 12-Week Safety Follow-Up (Part 1, OLE) Schedule of Assessments

Part 1 (OLE)	Week (± 7 days)		Unscheduled Visit ^c
	6 ^a	12/Early Withdrawal Visit ^b	
Concomitant medications	x	x	x
Adverse events	x	x	x
Urine pregnancy test ^d		x	
Partial physical examination		x	
PK sampling (serum)		x	
Anti-therapeutic antibody sample (serum) ^e		x	
PML neurologic examination ^f		x	

ATA= anti-therapeutic antibody; PK= pharmacokinetic; PML= progressive multifocal leukoencephalopathy.

- ^a Week 6 study assessments are to be made by telephone call and not by clinic visit.
- ^b If the patient discontinues prior to completion of the 12-week safety follow-up, the indicated assessments for the 12-week safety follow-up clinic visit should be performed as the early termination visit of the safety follow-up period.
- ^c Unscheduled visit for safety monitoring.
- ^d For women of childbearing potential, including those who have had a tubal ligation, perform a urine pregnancy test; if the urine pregnancy test result is positive, confirm with a serum pregnancy test.
- ^e If serum sickness or a clinically significant allergic drug reaction is suspected, Sponsor should be notified and serum for etrolizumab PK and ATAs should be drawn and sent to the central laboratory. ATA samples may be used for PK and/or exploratory PD assessments.
- ^f PML neurologic examination consists of the PML Subjective Checklist and the PML Objective Checklist. Administer before other assessments as per [Appendix 5](#).

Appendix 3

Extended Progressive Multifocal Leukoencephalopathy Safety Monitoring (Part 2, SM) Schedule of Assessments

Part 2 (SM)	92-week Extended PML Monitoring Period ^a	
	24, 48, 68, and 92 Weeks after Patient Discontinuation from Study OR Symptom-Driven Unscheduled Telephone Call ^b OR Early Termination ^c	Unscheduled Visit ^d
PML Subjective Checklist (telephone only)	x	
PML Objective Checklist ^e		x
Adverse event reporting to the Sponsor ^f	x	x

OLE-SM= open-label extension–safety monitoring; PML = progressive multifocal leukoencephalopathy.

Note: The extended PML monitoring period is to be conducted for patients completing or discontinuing from OLE-SM Part 1 AND for patients entering OLE-SM Part 2 from blinded Phase III studies after completion of 12-week safety follow-up in the Phase III studies AND for patients entering OLE-SM Part 2 from the Phase II OLE study (GA27927).

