4.1 GENERAL CONSIDERATIONS

4.1.1 Analysis of Study Conduct

The number of patients who enrolled in Part 1 (OLE) and Part 2 (SM) will be tabulated. The number of patients who discontinued early (early discontinuation of OLE treatment or early termination from the study) or completed the study will be tabulated.

Reasons for early discontinuation of treatment or early termination from the study will be listed and summarized. Any eligibility criteria exceptions and other major protocol deviations will also be summarized. The data will also be summarized by origin of the patient (i.e., by original Phase II OLE protocol or Phase III controlled protocol).

Since Part 1 (OLE) of GA28951 was terminated by the Sponsor on 15th February 2022, no patients are expected to reach treatment completion. As a result of this, the end of Part 1 (OLE) of GA28951 is defined from the last dose date in GA28951 on 15th May 2022.

In summary, the following will be summarized for GA28951 Part 1 (OLE):

- Analysis populations
- Patient disposition
- Study treatment completion/discontinuation
- Study completion/discontinuation
- Major protocol deviations
- Exposure

Treatment Labels

For the OLE population, the only treatment arm to be summarized is:

Group	Patients Included
OLE Etrolizumab	Patients in the OLE population who receive at least one dose of etrolizumab in Study GA28951 Part 1 (OLE)

OLE = Open-Label-Extension

Part 1 (OLE) Day 1

OLE Study Day 1 is defined as the day patient has the first receipt of study drug in GA28951 Part 1 (OLE).

Baseline

For patients who were previously enrolled in one of the Phase III studies, baseline is defined as the last available assessment prior to first receipt of study drug in the Induction Phase of the parent studies: GA28948, GA28949, GA28950, GA29102, and GA29103.

For patients who were previously enrolled in the Phase II trial GA27927, baseline is defined as the last available assessment prior to first receipt of study drug in their parent trial ABS4986g.

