4.2 SAFETY ANALYSES

Safety data will be assessed through descriptive summaries using the OLE population. All data available up until the clinical cut-off date (CCOD) will be reported

Safety evaluations for the OLE population will include data from the first dose of treatment in Part 1 until the patient completes/withdraws from the Part 1 (OLE) of the study GA28951, this includes any 12-week safety follow-up data.

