where the total patient-years at risk is the sum over all patients of the time intervals (in years) from the first dose of study treatment in Part 1 (OLE) until the patient completes/withdraws from the study (including the 12-week safety follow-up, if applicable). Only treatment emergent AEs with an onset date after the first dose of open label etrolizumab in GA28951 will be included within these outputs.

All summary tables and listings will report AEs using the OLE population.

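### SAP 4.2.3.5 ends the concomitant-medication summary 7 days after the last OLE dose, while adverse events and patient-years run through the 12-week safety follow-up, so therapy started from Day 8 is missing from the planned medication summaries

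*SAP*

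**What the plan says.** - **Medication summary.** SAP 4.2.3.5 covers use "from first dose of OLE study drug through to 7 days after last dose of OLE study drug", split by class and preferred name. SAP 4.4, on changes from the protocol, gives no reason for the 7-day limit.
- **Adverse events.** SAP 4.2 takes safety data from the first Part 1 dose until the patient completes or leaves Part 1, and "this includes any 12-week safety follow-up data". SAP 4.2.4 also ends the safety timeframe after follow-up.
- **Rates.** In SAP 4.2.2, time at risk ends when the patient completes or withdraws, "including the 12-week safety follow-up, if applicable".
- **Label.** SAP 4.1.1 states that "the only treatment arm to be summarized is" OLE Etrolizumab.
- **Collection.** Protocol Appendix 2, "12-Week Safety Follow-Up (Part 1, OLE) Schedule of Assessments", marks concomitant medication at the Week 6 call, at the Week 12 or early withdrawal visit, and at unscheduled visits. Protocol 4.2.1.1 has all concomitant medication in Part 1 recorded on the eCRF. It defines concomitant therapy as running up to completion of, or early withdrawal from, treatment.
- **Who enters follow-up.** Under Protocol 3.1.1.1, everyone finishing or leaving Part 1 does. Patients given prohibited rescue therapy "are to be withdrawn into the 12-week safety follow-up".

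**The concern.** The weeks after the last dose are when a patient who has stopped etrolizumab could begin another treatment for UC. Protocol 3.1.1.1 expressly sends patients who took prohibited rescue therapy into this period. SAP 4.1.1 adds that the sponsor terminated Part 1 on 15 February 2022, with last dosing on 15 May 2022, so all patients still on drug reach the follow-up within a few months of each other.

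A serious or opportunistic infection that begins after a new immunosuppressive agent would be tabulated as an OLE Etrolizumab event. The medication tables would not show that agent if it was started from Day 8. The SAP plans no separate output for later therapy, no marker on events that follow it, and no split of events into on-treatment and follow-up. SAP 4 makes safety the core of the synoptic report, so a reader would want to see the overlap.

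**Working it through.** The plan states no figure to reproduce. The check compares the two reporting windows.

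**Inputs**
- Medication window after last dose: 7 days (SAP 4.2.3.5).
- Safety follow-up: 12 weeks = 84 days (SAP 4.2 and 4.2.2).
- Dosing interval: 4 weeks = 28 days (Protocol 3.1.1.1).
- Early withdrawal from treatment visit: up to 30 days after the last dose (Protocol Appendix 1, footnote d). Protocol 4.4.3.2 places the 12-week follow-up after that visit, so the AE window after last dose may be 84 days or as long as 30 + 84 = 114 days.

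**Step 1. Stretch with AE counting but no medication summary** (AE window − 7)
- Follow-up from last dose: 84 − 7 = 77 days, and 77/84 = 91.7% of the post-dose window.
- Follow-up from a visit 30 days after last dose: 114 − 7 = 107 days, and 107/114 = 93.9%.

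For a patient last dosed on 15 May 2022, medication reporting ends on 22 May. On the 84-day reading, AE reporting ends about 7 August.

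**Step 2. The final dosing interval**

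7/28 = 25% is covered and 21/28 = 75% is not. Suppose a patient starts a prohibited agent on Day 10 after a dose. Protocol 4.2.2 and 4.5.1.1 require study drug to stop, so that dose becomes the last one and Day 10 lies outside the table. If such starts were spread evenly over the interval (an assumption), three quarters would be missed.

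**Step 3. Comparison with the protocol's own end point**

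Protocol 4.2.1.1 carries concomitant therapy to completion of, or early withdrawal from, treatment. For a patient who stops early, the withdrawal visit may be up to 30 days after the last dose, so the SAP window can close up to 30 − 7 = 23 days sooner.

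**Step 4. Share of a patient's whole AE time**

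Share = 77/(treatment days + 84), or 107/(treatment days + 114). The durations below are assumed.

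| Last dose at | Follow-up from last dose | Follow-up from a visit 30 days later |
|---|---|---|
| Week 24 (168 days) | 77/252 = 30.6% | 107/282 = 37.9% |
| Week 52 (364 days) | 77/448 = 17.2% | 107/478 = 22.4% |
| Week 108 (756 days) | 77/840 = 9.2% | 107/870 = 12.3% |
| Week 208 (1456 days) | 77/1540 = 5.0% | 107/1570 = 6.8% |

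**Step 5. A rate without the later events**

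The SAP rate is 100 × E/T, where E is events and T is patient-years. Let f be events with onset on or after the start of the new therapy and t the patient-years from that start. Deleting f alone gives (E − f)/T. Whenever t > 0 this is lower than (E − f)/(T − t), so it understates the rate before the new therapy. Events and time have to be censored together.

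**The case against.** The strongest reply is that the SAP's window is anchored to treatment, as Protocol 4.2.1.1's definition is, and that a single-arm descriptive study may properly count every event through follow-up whatever therapy comes next. Much of this stands. Counting AEs for 12 weeks is sound: Protocol 5.1.1.7 equates that period with "approximately 5 half-lives (approximately 12 weeks) after final study drug administration". It does not justify Day 7, however, since Step 3 shows that the cut can precede even the protocol's treatment-based end point.

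A reader might go further and infer any of the following. The documents do not support them.
- **The later therapy is hidden, or attribution is biased.** The data are collected, and any medication in use by Day 7 is still tabulated. SAP 4.1.1 summarises discontinuation reasons and major deviations, SAP 4.2.2 plans AE listings, and causality assessment under Protocol 5.4.5 weighs concomitant medication. These do not replace a link between medication and events, but they rule out concealment. No direction or size of bias can be shown.
- **About 92% of events are affected.** That figure is a share of days after the last dose. As a share of total AE time it falls to 9–12% for a last dose at Week 108.
- **Day 7 fails because much of the drug remains in the body.** A definition of concomitant use need not rest on elimination, and the only half-life figure comes from guidance on live vaccines.
- **Malignancies should be re-attributed.** About 11 weeks under a successor agent is short for that, so malignancies are left out of the proposed flag.

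**Conclusion.** The mismatch holds. The medication summary stops 77 days before AE reporting does, or up to 107 days before if follow-up starts at a withdrawal visit 30 days after the last dose. It covers a quarter of the final dosing interval, so it can omit the prohibited agent that led to withdrawal. This is a reporting gap in a stated rule, using data already scheduled for collection.

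The window arithmetic rests on the documents alone. The shares of AE time rest on assumed treatment durations. The documents do not say how many patients start another therapy from Day 8, so the number of affected events is unknown.

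**What to change.** 1. In SAP 4.2.3.5, extend the window to the end of the 12-week safety follow-up.
2. Tabulate separately the medications first started after the last OLE dose.
3. In the listings of SAEs, serious infections, opportunistic infections and AESIs, flag events with onset on or after the start of a therapy named in Protocol 4.2.2.
4. A sensitivity rate is optional. If one is shown, censor both events and patient-years at the start of that therapy.

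Leave the AE window and the main AE tables unchanged. No clinical rule is touched and no new data are needed.

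The cost is a wording change, one table split and a derivation that matches medication and event start dates. That derivation needs a rule for partial dates, which the SAP does not give. Outputs become slightly longer.

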4.2.4 Open-Label Extension Timeframe

For the open-label extension population, the safety reporting timeframe is defined to capture safety information within the OLE treatment period only. It begins at first dose of study drug in Study GA28951 Part 1 (OLE). The end of the time-frame coincides with the last patient's last visit, this includes safety follow-up in Study GA28951 Part 1 (OLE).

All outputs focus only on safety events after first dose in Study GA28951; these can be handled by flagging events that arise during the OLE treatment period in a manner similar to the identification of treatment-emergent AEs.

4.3 INTERIM ANALYSES

There are no planned interim analyses for study GA28951.

4.4 CHANGES TO PROTOCOL-PLANNED ANALYSES

The incidence of ATAs to etrolizumab was extensively evaluated in the Ulcerative Colitis and Crohn's Disease within the phase 3 program where, no obvious impact on injection site reactions or other relevant safety parameters such as hypersensitivity was found. Following this evaluation ATAs has been de-prioritised from a safety objective and outcome measure in GA28951 to an exploratory objective and outcome measure.

5. SUPPORTING DOCUMENTATION

This section is not applicable, since there is no additional supporting document.

